Appendix 3 Insomnia Daytime Symptoms and Impacts Questionnaire

Daridorexant (ACT-541468) Insomnia and comorbid nocturia Protocol ID-078A401 Version 3 4 September 2023, page 95/122

[figure not shown]
EU CT 2022-501246-30-00 Doc No D-23.307

Daridorexant (ACT-541468) Insomnia and comorbid nocturia Protocol ID-078A401 Version 3 4 September 2023, page 96/122

Confidential

EU CT 2022-501246-30-00 Doc No D-23.307

Daridorexant (ACT-541468) Insomnia and comorbid nocturia Protocol ID-078A401 Version 3 4 September 2023, page 97/122

EU CT 2022-501246-30-00 Doc No D-23.307

Daridorexant (ACT-541468) Insomnia and comorbid nocturia Protocol ID-078A401 Version 3 4 September 2023, page 98/122

Confidential

Appendix 4 Insomnia Severity Index[®]

CCI	

Daridorexant (ACT-541468) Insomnia and comorbid nocturia Protocol ID-078A401 Version 3 4 September 2023, page 99/122

[figure not shown]
Confidential

Appendix 5 Global Scales

11	
CCI	

Daridorexant (ACT-541468) Insomnia and comorbid nocturia Protocol ID-078A401 Version 3 4 September 2023, page 100/122

[figure not shown]
EU CT 2022-501246-30-00 Doc No D-23.307

Daridorexant (ACT-541468) Insomnia and comorbid nocturia Protocol ID-078A401 Version 3 4 September 2023, page 101/122

Confidential

EU CT 2022-501246-30-00 Doc No D-23.307

Daridorexant (ACT-541468) Insomnia and comorbid nocturia Protocol ID-078A401 Version 3 4 September 2023, page 102/122

Confidential

[figure not shown]
Appendix 6 EQ-5D-3L

CCI		

Daridorexant (ACT-541468) Insomnia and comorbid nocturia Protocol ID-078A401 Version 3 4 September 2023, page 103/122

Confidential

[figure not shown]
EU CT 2022-501246-30-00 Doc No D-23.307

Daridorexant (ACT-541468) Insomnia and comorbid nocturia Protocol ID-078A401 Version 3 4 September 2023, page 104/122

Confidential

Appendix 7 ICIQ-NQoL

Daridorexant (ACT-541468) Insomnia and comorbid nocturia Protocol ID-078A401 Version 3 4 September 2023, page 105/122

[figure not shown]
Confidential

EU CT 2022-501246-30-00 Doc No D-23.307

Daridorexant (ACT-541468) Insomnia and comorbid nocturia Protocol ID-078A401 Version 3 4 September 2023, page 106/122

[figure not shown]
EU CT 2022-501246-30-00 Doc No D-23.307

Daridorexant (ACT-541468) Insomnia and comorbid nocturia Protocol ID-078A401 Version 3 4 September 2023, page 107/122

Confidential

[figure not shown]
Appendix 8 ICIQ-MLUTS

Daridorexant (ACT-541468) Insomnia and comorbid nocturia Protocol ID-078A401 Version 3 4 September 2023, page 108/122

Confidential

EU CT 2022-501246-30-00 Doc No D-23.307

Daridorexant (ACT-541468) Insomnia and comorbid nocturia Protocol ID-078A401 Version 3 4 September 2023, page 109/122

[figure not shown]
Confidential

EU CT 2022-501246-30-00 Doc No D-23.307

[figure not shown]
Daridorexant (ACT-541468) Insomnia and comorbid nocturia Protocol ID-078A401 Version 3 4 September 2023, page 110/122

EU CT 2022-501246-30-00 Doc No D-23.307

Daridorexant (ACT-541468) Insomnia and comorbid nocturia Protocol ID-078A401 Version 3 4 September 2023, page 111/122

EU CT 2022-501246-30-00 Doc No D-23.307

Daridorexant (ACT-541468) Insomnia and comorbid nocturia Protocol ID-078A401 Version 3 4 September 2023, page 112/122

Confidential

[figure not shown]
EU CT 2022-501246-30-00 Doc No D-23.307

Appendix 9 ICIQ-FLUTS

CCI	

Daridorexant (ACT-541468) Insomnia and comorbid nocturia Protocol ID-078A401 Version 3 4 September 2023, page 113/122

EU CT 2022-501246-30-00 Doc No D-23.307

Daridorexant (ACT-541468) Insomnia and comorbid nocturia Protocol ID-078A401 Version 3 4 September 2023, page 114/122

[figure not shown]
EU CT 2022-501246-30-00 Doc No D-23.307

Daridorexant (ACT-541468) Insomnia and comorbid nocturia Protocol ID-078A401 Version 3 4 September 2023, page 115/122

Confidential

EU CT 2022-501246-30-00 Doc No D-23.307

Daridorexant (ACT-541468) Insomnia and comorbid nocturia Protocol ID-078A401 Version 3 4 September 2023, page 116/122

Confidential

Appendix 10 Columbia Suicide Severity Rating Scale[©] (C-SSRS[©])

CCI	i O	

Daridorexant (ACT-541468) Insomnia and comorbid nocturia Protocol ID-078A401 Version 3 4 September 2023, page 117/122

Confidential

EU CT 2022-501246-30-00 Doc No D-23.307

Confidential

Appendix 11 Forbidden medications

Forbidden (F) or restricted (R) concomitant medications due to CNS side effects and DDI interactions.

To be eligible, subjects must not be treated with CNS-active drugs for 5 half-lives of the respective drug or 2 weeks prior to Visit 2 (whichever is longer) until 24 hours after study treatment discontinuation.

Drug Class	Examples	Forbidden	Comment
		/ Restricted	
Anticholinergics	e.g., oxybutynin, solifenacin	R	The use of anticholinergics are allowed if initiated at least 1 month prior to Visit 1 and planned to remain stable during the study.
Antihistamines	Sedating: e.g., carbinoxamine, triprolidine HCl, azatadine, chlorpheniramine, doxylamine, hydroxyzine, ketotifen, promethazine & timeprazine, diphenhydramine HCl, dimenhydrinate	F	
Psychotropics	Stimulants: e.g., amphetamine derivatives, ephedrine derivatives, modafinil, armodafinil, methylphenidate, aripiprazole, pramipexole, levodopa, guanfacine, atomoxetine	F	
	Antidepressants: e.g., bupropion, citalopram, doxepin, duloxetine, escitalopram, fluoxetine, fluvoxamine, nefazodone, paroxetine, sertraline, trazodone,	F	
	amitriptyline, clomipramine, desipramine, imipramine, mirtazapine, nortriptyline, trimipramine, venlafaxine, moclobemide, selegiline Antipsychotics, including depot neuroleptics: e.g., quetiapine, olanzapine, haloperidol, loxapine, molindone, thiothixene, fluphenazine, mesoridazine	F	

Daridorexant (ACT-541468) Insomnia and comorbid nocturia Protocol ID-078A401 Version 3

Confidential

EU CT 2022-501246-30-00 Doc No D-23.307

4 September 2023, page 119/122

Drug Class	Examples	Forbidden	Comment
		/ Restricted	
	Anxiolytics: e.g., alprazolam, buspirone, clorazepate, diazepam, flurazepam, lorazepam, midazolam,	F	
	quazepam, temazepam, triazolam Hypnotics: e.g., ramelteon, suvorexant, lemborexant, zolpidem	F	
	Cholinesterase inhibitors: e.g., donepezil, galantamine Mood stabilizers , e.g., carbamazepine, gabapentin, lithium, oxcarbazepine, pregabalin, valproic acid,	F	
	tiagabine Opioids/Narcotics : e.g., codeine, oxycodone, heroin, marijuana	R	Use of narcotics for pain relief must be avoided if there are effective alternative medications (such as NSAIDs)
	Centrally acting muscle relaxants with psychotropic effects: e.g., methocarbamol, tetrazepam	R	Use of centrally acting muscle relaxants must be avoided if there are effective alternative medications (such as NSAIDs)
	Herbal preparations with possible psychotropic effects: e.g., St John's Wort	F	,
	Others: e.g., tryptophan, melatonin, clonidine, dextromethorphan	F	
Anticonvulsants	Barbiturates, benzodiazepines, GABA analogs, hydantoins phenyltriazines (e.g., lamotrigine) succinimides (e.g., ethosuximide)	F	
Alpha Blockers:	Silodosin, tamsulosin	R	Allowed if initiated at least 1 month prior to Visit 1 and planned to remain stable during the study
5-Alpha-Reductase-Inhibitors	e.g., finasteride, dutasteride	R	5-alpha-reductase-inhibitors are allowed if initiated at least 6 months prior to Visit 1

Daridorexant (ACT-541468) Insomnia and comorbid nocturia Protocol ID-078A401 Version 3 4 September 2023, page 120/122

Confidential

Comment

Drug Class Examples Forbidden / Restricted

		/ Restricted	and planned to remain stable during the study
Other	Desmopressin	R	Desmopressin is allowed at therapeutic doses of 25–50 mg, only if initiated at least 6 months prior to Visit 1 and planned to remain stable during the study
	Systemic glucocorticoids: e.g., dexamethasone, methylprednisone, prednisone	F	Inhaled/topical corticosteroids are permitted
	Diet pills (prescription and OTC)	F	
	Pseudoephedrine	R	Use as nasal decongestant is allowed

GABA = gamma-aminobutyric acid; NSAID = non-steroidal anti-inflammatory drug; OTC = over-the-counter.

Non-exhaustive list of forbidden concomitant medications and diets due to potential drug interactions with CYP3A4 (moderate and strong inhibitors, inducers).

Those medications must be discontinued no later than 2 weeks or 5 half-lives (whichever is longer) prior to Visit 2 and are forbidden until 24 hours after study treatment discontinuation.

Inhibitors of CYP3A4	Inducers of CYP3A4
HIV antivirals: atazanavir, boceprevir, cobicistat, darunavir, delaviridine, fosamprenavir, indinavir, lopinavir, nelfinavir, ritonavir, saquinavir, telaprevir	HIV antivirals: efavirenz, etravirine
Antibiotics: ciprofloxacin, clarithromycin, erythromycin, norfloxacin, quinupristin, telithromycin, troleandomycin	Antibiotics: nafcillin, rifabutin, rifampin
Antifungal: fluconazole, itraconazole, ketoconazole, posaconazole, voriconazole	
CNS-active: fluvoxamine, nefazodone	CNS-active: carbamazepine, fenobarbital, modafinil, phenytoin, St. John's Wort
Cardiovascular: amiodarone, diltiazem, dronedarone, verapamil	Cardiovascular: bosentan
Aprepitant, conivaptan, cimetidine, imatinib	

[figure not shown]
CNS = central nervous system; CYP = cytochrome P450; HIV = human immunodeficiency virus.

Confidential

Appendix 12 Treatment satisfaction questionnaire

Treatment satisfaction:

"Please mark the number that best describes your overall satisfaction with the study medication **during** the clinical study (Mark one number only)"

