3.2.14 Treatment satisfaction [Appendix 12]

The NRS collects information on the treatment satisfaction during the clinical trial by asking the subjects to mark the number that best describes the overall satisfaction.

Self-reported treatment satisfaction is assessed in the morning of Visit 4, Visit 8 and PEOT on the electronic device.

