3.2.16 Narrative [Appendix 14]

The subjects will complete a free text question on the electronic device at Visit 1, Visit 4, Visit 8 and PEOT. They will also be asked to write a short text about their overall feeling.

At Visit 1 the narrative question will refer to the time before being on treatment, while at Visits 4, 8 and PEOT the narrative will refer to the time while on treatment.

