Daridorexant (ACT-541468) Insomnia and comorbid nocturia Protocol ID-078A401 Version 3

4 September 2023, page 44/122

Objectives	Endpoints in period I and period II			
	• Changes from baseline to Week 1, Week 2, Week 3, and Week 4 in Patient Global Impression of Change (daytime and nighttime symptoms)			
	 Change from baseline to Week 4 in Patient Global Assessment of Disease Severity (daily life) Change from baseline to Week 4 in Patient Global Impression of Change (daily life) 			
	• Change from baseline to Week 2 and Week 4 in EQ-5D-3L score			
	• Treatment satisfaction at Week 4 assessed via NRS			
	• Treatment period preference at Visit 8 (EOTP II)			
To explore a) the sensitivity of the IDSIQ to detect clinical changes in this study population and b) the use of narratives to report subject's perception of treatment effect	 The change from baseline to Week 1, Week 2, Week 3, and Week 4 in all IDSIQ domains The subjects will be asked to complete a narrative at the end of each treatment period. More details on the analysis will be provided in the SAP. 			
To assess the safety and tolerability of daridorexant	Safety endpoints			
	Safety monitoring will include:			
	• Occurrence of TEAEs up to 5 days after EOTP I and/or EOTP II.			
	• Occurrence of treatment emergent AESIs up to 5 days after EOTP I and/or EOTP II.			
	• Occurrence of treatment-emergent serious adverse events up to 5 days after EOTP I and/or EOTP II.			
	Occurrence of TEAEs leading to premature discontinuation of the study and/or treatment.			
	• Change from baseline to EOTP I and EOTP II in vital signs (systolic blood pressure, diastolic blood pressure, and pulse rate).			
	• Change from baseline to EOTP I and EOTP II in morning sleepiness as determined by the scores on the VAS in the morning.			
	• Occurrence of suicidal ideation, suicidal behavior, and/or self-injurious behavior with / without suicidal intent based on the C-SSRS [©] at Visit 1, Visit 4, Visit 5, Visit 8, and Visit 9.			

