# 6.3.3.6 Treatment satisfaction

The Numeric Rating Scale collects information regarding treatment satisfaction during the clinical trial by asking the subjects to mark the number that best describes overall satisfaction on a scale from 0 ('Not at all satisfied') to 10 ('Extremely satisfied). Self-reported treatment satisfaction is assessed on the morning of Visit 4 and Visit 8 on the eDiary.

A paired t-test will be applied to the within-subject differences (daridorexant 50 mg vs placebo) to test for differences between the two treatments. The output will contain the mean estimate (including 95% CI) and the associated p-value.

Treatment satisfaction will be summarized descriptively by treatment.

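### The treatment-satisfaction item names no treatment period, so the Visit 8 answer may reflect both cross-over treatments and the planned paired difference may be attenuated

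*Protocol*

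**What the plan says.** **The question.** Appendix 12 asks for the number that "best describes your overall satisfaction with the study medication during the clinical study". Protocol 3.2.14 describes the item with the same frame: it "collects information on the treatment satisfaction during the clinical trial". SAP 6.3.3.6 repeats that frame and adds the 0 to 10 scale.

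**The timing.** Protocol 3.2.14: "Self-reported treatment satisfaction is assessed in the morning of Visit 4, Visit 8 and PEOT on the electronic device". Visit 4 ends Period I and Visit 8 ends Period II.

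**The endpoint.** Table 3 in protocol 3.4 lists "Treatment satisfaction at Week 4 assessed via NRS" in the column headed "Endpoints in period I and period II". The intended quantity is therefore one value for each period.

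**The analysis.** SAP 6.3.3.6 states: "A paired t-test will be applied to the within-subject differences (daridorexant 50 mg vs placebo"). The output is a mean estimate with 95% CI and a p-value.

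No section of either document limits the Visit 8 answer to Period II.

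**The concern.** The question put to the subject and the quantity analysed do not match. The analysis needs a rating of Period I treatment and a separate rating of Period II treatment. The item asks about the study medication over the study. By Visit 8 the subject has taken both daridorexant and placebo, so a literal answer is some blend of the two.

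This would act like carry-over, but it would come from the wording of the question, and the 14–21 day washout cannot remove it. At stake is the answer to one named objective, treatment satisfaction. Its mean difference would be read as satisfaction with daridorexant against placebo. Afterwards, nobody could tell a small effect from a blended answer.

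Other instruments in the protocol are bounded: the IDSIQ refers to today, the ISI to 2 weeks and the ICIQ-NQoL to 4 weeks. The preference item in Appendix 13 names Period 1 and Period 2.

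**Working it through.** **The plan's own figures.** Neither document gives an effect, SD or power for satisfaction, so there is nothing to reproduce on this endpoint. To check the power method (paired t-test, noncentral t, n = 50, two-sided 0.05), I applied it to the primary endpoint in protocol 9.4. A difference of 26 min with SD 44 min gives 98.4% (stated: at least 90%). A difference of 20 min gives 88.3% (stated: at least 80%).

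**Inputs.** From the documents: two sequences at 1:1, about 50 subjects, ratings at Visits 4 and 8. Assumed: the weight w on Period II at Visit 8, shown from 0.5 to 1. For power, also assumed: a paired test with 80% power when w = 1 (standardised difference 0.404), and a share f of the variance of the difference that is reporting noise.

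**Effect on the mean.** Let A and B be a subject's ratings of daridorexant and placebo.

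- Daridorexant then placebo: Visit 4 = A and Visit 8 = wB + (1−w)A. Daridorexant minus placebo = A − [wB + (1−w)A] = w(A−B).
- Placebo then daridorexant: Visit 4 = B and Visit 8 = wA + (1−w)B. Daridorexant minus placebo = [wA + (1−w)B] − B = w(A−B).

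The factor is w in both sequences, so balanced sequences do not cancel it and a period term would not remove it. A true difference of 1.0 point has expected estimate 1.00 at w = 1, 0.75 at w = 0.75 and 0.50 at w = 0.5. A simulation of both sequences with a realised true mean of 0.99 gave 0.99, 0.74 and 0.50.

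**Effect on power (illustrative).** Set the variance of the difference to 1 at w = 1. Blending shrinks the true part by w² and leaves the noise unchanged, so the SD is √[w²(1−f) + f] and the standardised difference is 0.404w / √[w²(1−f) + f].

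| w | f = 0 | f = 0.5 | f = 1 |
|---|---|---|---|
| 1 | 80% | 80% | 80% |
| 0.75 | 80% | 66% | 56% |
| 0.5 | 80% | 43% | 29% |

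Example, w = 0.5 and f = 0.5: SD = √(0.125 + 0.5) = 0.791, standardised difference = 0.202 / 0.791 = 0.256, power 43%. With no reporting noise the mean and SD shrink together, so power stays the same and only the estimate and its CI are scaled down.

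**Precision of a Visit 4-only comparison.** Keep the SD of the paired difference at 1 and let r be the within-subject correlation (assumed). The SD of a single rating is 1/√[2(1−r)]. At r = 0.5 this is 1, so the standard error with 25 against 25 subjects is √(2/25) = 0.283, against 1/√50 = 0.141 for the paired test: twice as large. Power for the same effect is about 29%, and 38% to 19% for r = 0.3 to 0.7.

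**The case against.** **The context points to the current period.** The item is answered at the end of each period, at the visit where that period's tablets are returned, and is listed as a Week 4 endpoint in each period. A subject may well take the study medication to mean the tablets just finished. At Visit 8 a separate item asks the subject to choose between the two periods. If everyone rates the latest period, w = 1 and there is no bias. This stands: blending is the literal reading of the text, not an observed fact.

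**The direction is not certain.** A subject who has tried both treatments may rate the second by contrast with the first. That acts like w > 1 and would inflate the difference. Nothing in the documents rules it out.

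**The size has almost no trial input.** Only n = 50 comes from the plan. The case f = 1 requires that no variation in the difference between subjects be real.

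**The endpoint is minor.** The testing strategy contains only sTST, and no secondary endpoints are defined. Treatment preference gives a separate comparison that does name the periods.

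**The remedy may come late and is imprecise.** SAP version 2 already describes eDiary collection of the PGA-S in the past tense, and the Visit 4-only comparison is weak.

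These points limit how strongly the conclusion can be stated and how much weight the supportive analysis can bear. They do not remove the mismatch between the item and its use.

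**Conclusion.** The point holds as a mismatch with a possible bias. The item is framed by the study, the analysis needs a rating framed by the period, and no text bridges the two at Visit 8. For any w below 1 the daridorexant-minus-placebo difference is multiplied by w in both sequences. The range shown, from no bias to a halved estimate, rests on assumed weights of 1 down to 0.5. Only the Visit 8 rating is affected, and the endpoint is exploratory.

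A reader might infer three stronger things that the documents do not support:

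- That the satisfaction effect will be too small. This needs w < 1, which is not shown.
- That the test will lose power. Power falls only if reporting noise is present, and the percentages above are illustrations.
- That the free-text narrative has the same fault. Protocol 3.2.16 describes it without naming a period, but the text of Appendix 14 is not shown, Table 3 places it at the end of each treatment period, and its analysis is left to a separate plan.

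**What to change.** Reword the item in Appendix 12, and its description in protocol 3.2.14 and SAP 6.3.3.6, to refer to *the study medication you took during this treatment period*, identically at Visit 4, Visit 8 and PEOT. The cost is one changed sentence on the electronic device, with its translations.

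If data were already collected with the printed text, make two changes in SAP 6.3.3.6:

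- State that the Visit 8 rating may reflect both periods, so the paired difference may be attenuated.
- Add a comparison of Visit 4 ratings between the two sequences. It is free of blending because only one treatment has been taken by then. Label it supportive and report it beside the paired analysis, not in its place. With a standard error about twice that of the paired test at r = 0.5, a gap between the two estimates would be only weak evidence of blending.

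The second route costs one sentence and one two-sample summary of data already in hand.

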Appendix 13 Treatment period preference questionnaire

Treatment period preference

"Please specify which treatment period you preferred":
 □ Period 1 □ Period 2

Daridorexant (ACT-541468) Insomnia and comorbid nocturia Protocol ID-078A401 Version 3 4 September 2023, page 122/122

Confidential

EU CT 2022-501246-30-00 Doc No D-23.307

Appendix 14 Narrative

# Confidential

Statistical Analysis Plan for Clinical Study Report Version 2 Doc No D-24.149

# LIST OF ABBREVIATIONS AND ACRONYMS

AE	Adverse event
AESI	Adverse event of special interest
ATC	Anatomical Therapeutic Chemical
CI	Confidence interval
C-SSRS ©	Columbia Suicide Severity Rating Scale ©
eCRF	Electronic case report form
eDiary	Electronic diary
EOS	End-of-study
EOT	End-of-treatment
EOTP	End-of-treatment period
EQ-5D-3L	European Quality of Life 5 Dimensions 3 Level Version
FAS	Full analysis set
ICH	International Council for Harmonisation
ICIQ	International Consultation on Incontinence Questionnaire
ICIQ-FLUTS	ICIQ female lower urinary tract symptoms
ICIQ-MLUTS	ICIQ male lower urinary tract symptoms
ICIQ-NQoL	ICIQ Nocturia Quality of Life
IDSIQ	Insomnia Daytime Symptoms and Impacts Questionnaire
IMP	Investigational Medicinal Product
$\mathrm{ISI}^{\circledcirc}$	Insomnia Severity Index ©
LS	Least squares
MedDRA	Medical Dictionary for Regulatory Activities
MMRM	Mixed model for repeated measures
PD	Protocol deviation
PGA-S	Patient Global Assessment of Disease Severity
PGI-C	Patient Global Impression of Change
PPS	Per-protocol set
PT	Preferred term
RND	Randomized analysis set
SAE	Serious adverse event
SAF	Safety analysis set

Daridorexant (ACT-541468)		Statistical Analysis Plan		
ID-078A401	Confidential	for Clinical Study Repor		
30 May 2024	Confidential	Version 2		
Page 7/50		Doc No D-24.149		

SCR	Screened analysis set	
SOC	System organ class	
sTST	Subjective total sleep time	
TEAE	Treatment-emergent adverse event	
TP I	Treatment Period I	
TP II	Treatment Period II	
V	Visit	
VAS	Visual analog scale	
WHO	World Health Organization	

#### 1 INTRODUCTION

This statistical analysis plan describes the analyses and data presentation for the clinical study report prepared for study ID-078A401 in detail. The analyses will be conducted once all randomized subjects have completed the study and the database has been locked.

Obvious corrections to address minor formatting errors or spelling mistakes may be performed at the time of analysis without amending this and related documentation (e.g., mock shells).

Data will be analyzed by Idorsia and designated contract research organizations supervised by Idorsia using SAS® version 9.4 or higher and R version 3.4.3 or higher.

This statistical analysis plan is based on Version 3 of the protocol of ID-078A401, dated 4 September 2023 [D-23.307, Table 1].

Table 1 Study documents

Document	Date, Version	
Clinical Study Protocol	4SEP2023, Version 3	
eCRF specifications	14NOV2023, Version 5	
Protocol deviation list	14MAY2024, Version 6	

eCRF = electronic case report form.

